Reduced phosphate uptake, on the other hand, depends on the depletion of phosphate groups by a specific isoform of phosphofructokinase expressed by enterocytes (13); therefore, the reduction in the ATP/AMP ratio leads to inhibition of the Na/P transporter. This mechanism would also occur at the renal level where inhibition of this transporter promotes urinary excretion of phosphorus (14).

Recent studies show how an increase in dietary fructose appears to be responsible for the onset of several obesity-associated diseases; foremost among them NAFLD, which is increasing in tandem with obesity even in the pediatric population. The aim of this study is mainly to understand the effect of fructose on the molecular events contributing to pediatric development, as this could be an important target to address the clinical and social problems arising from its prevalence in pediatric age.

AIMS OF THE STUDY

The primary aim of this study is to evaluate the effects of fructose intake in a group of preschool children and overweight or obese adolescents; in particular, to investigate the impact of fructose consumption in the development of liver complications, such as NAFLD, and its degree of severity, as well as its impact in other obesity-associated diseases. **In addition, the present study aims to describe the composition of bone metabolism according to the level of fructose consumption.** Secondly, by means of omics analysis (metabolomics and metaproteomic), the aim is to characterize the microorganisms present in the gastrointestinal tract and their microbial activity in relation to dietary habits, fructose intake and clinical parameters. Finally, sociodemographic and cultural factors, in the children and adolescents considered in the study, and in their families, will be surveyed.

STUDY DESIGN

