This study consists of two parts, the first phase involves the conduct of a cross-sectional study to assess the relationship between fructose consumption and the presence of NAFLD and the difference in several parameters, including anamnestic, clinical, auxological and hematochemical assays and the presence of the disease, and a second prospective part for the sociological evaluation one year after entering the study. It constitutes an extension of a study already approved by the University of Bari, approval of which is attached by the Independent Ethics Committee university hospital company "Consorziale Policlinico" with approval number CE/7331. The study involves the collaboration of three different units, respectively formed by the University of Eastern Piedmont (unit 1), University of Bari "A. Moro" (unit 2) and the University of Rome "Foro Italico" (unit 3). The first two units will enroll subjects with criteria of interest for the study. The University of Rome, on the other hand, will be concerned with the socioeconomic aspect of the study with the preparation of ad hoc questionnaires to be submitted to both children/adolescents and families.

Subjects

100 overweight or obese preschool children and adolescents visited at the Outpatient Clinic of Pediatric Endocrinology of the AOU Maggiore della Carità in Novara, at the Transition Endocrinology Outpatient Clinic of the SCDU Endocrinology and at the Outpatient Clinic of Pediatric Endocrinology "B.Trambusti" of the Giovanni XXIII Pediatric Hospital in Bari will be included in the study. Subjects will be selected continuously with adherence to the inclusion criteria from January 2024 until the end of December.

Inclusion criteria

- Children and adolescents with expression of informed consent according to art.2 quinque of Legislative Decree n.196/2003;
- Preschool children of both sexes aged 3 to 6 years and adolescents of both sexes aged 12 to 16 years;
- Children diagnosed with overweight (defined by BMI > 97th percentile for children younger than 5 years; and BMI > 85th percentile for children older than 5 years) or obesity (defined by BMI > 99th percentile for children younger than 5 years; and BMI > 97th percentile for children older than 5 years) (15,16).

Exclusion criteria

- Children and adolescents who are not in this age group;
- Children and adolescents with liver disease different than NAFLD;
- Children and adolescents with genetic type obesity or secondary obesity;

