- Quantitative and qualitative analysis of bone composition using quantitative ultrasonography (QUS). This instrument provides different parameters related to bone composition, specifically speed of sound (SOS) assessing bone density, broadband ultrasound attenuation (BUA) assessing trabecular structure, ultrasound peak amplitude assessing trabecular size, number of peaks assessing connectivity of the mineralized matrix structure, and fast wave energy and amplitude assessing elasticity.
- US ultrasound of the abdomen to evaluate hepatic steatosis, perivisceral and subcutaneous fat. The presence of hepatic steatosis (NAFLD) will be classified from stage 1 to stage 3 according to literature (19).

Clinic-auxological evaluation

- Anthropometric measurements, such as weight, height and BMI assessment according to STANDARD DEVIATION SCORE (SDS). Waist and hip circumference measurements.
- Measurement of blood pressure and heart rate.
- Analysis of body composition by bio-impedance analysis (BIA)

Laboratory evaluation, hematochemical assays

Subjects will undergo the following assessments after at least 12 hours of overnight fasting:

- OGTT (glucose-loading curve; glucose 1.75 g/kg per os at time 0', maximum dose 75 g), with basal and every 30 min blood glucose and insulin draws.
- Basal blood draw for c-peptide, AST, ALT, gamma-GT, fractional and total bilirubin, azotemia, creatinine, eGFR, HbAic, fructosamine, total cholesterol, HDL, triglycerides, TSH, FT3 and FT4, leptin, adiponectin, DPP4, uric acid.
- Basal blood sampling for PCR, advanced glycation products (AGEs), AGE receptor (RAGE) and advanced protein oxidation products (AOPPs),
- Basal blood sampling for assay of intermediate products of fructose metabolism (fructose-lysine)
- Calcium, phosphorus, 25-OH vitamin D, PTH, osteocalcin, RANKL, osteoprotegerin, bone isoenzyme alkaline phosphatase, telopeptide C-terminal collagen type I (CTX), intact procollagen amino terminal type 1 (P1NP), IL-6, IL-1beta, biochemical parameters needed to assess bone metabolism.

They will, in addition, be performed:

- A urinalysis and 24-hour urine collection for evaluation of fructose metabolites in urine.
- Fecal sample for metabolomics and metaproteomic analysis.

ANALYSIS BY BIOCHEMICAL, HORMONAL AND MASS SPECTROMETRY PARAMETERS

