Descriptive statistics will be calculated in order to summarize the sociodemographic, perceptual, anthropometric, dietary, clinic-auxological, anamnestic and laboratory characteristics of the children included in the study.

Categorical variables will be summarized by absolute frequencies and percentages while numerical variables as mean and standard deviation (SD) or median and interquartile range (Q1-Q3) if not normally distributed according to the Shapiro Wilks test and quantile plot observation. The chi-square test or the corresponding nonparametric Fisher's test will be used to test the association between categorical variables and the presence of NAFLD while the t-test or the Mann-Whitney test will be used to test the difference in fructose consumption between children with NAFLD and those without the disease as well as the presence of differences between the two groups for the other numerical variables. The positive false discovery rate method will be used to account for the presence of multiple tests. Based on the number of NAFLD events observed, stratified analysis by age group (preschool age vs. adolescents) and center will be evaluated. **Regarding the assessment of bone metabolism, mean and standard deviation (SD) or median and interquartile range (Q1-Q3) of the parameters provided by the QUS overall and separately for high and low fructose consumption (below vs above median consumption) will be calculated.**

Microbiota analysis

Initially, an exploratory analysis of the relative abundance of the genera of bacteria in the microbiota will be carried out. The relative abundance of each species detected in the fecal samples will be represented by heatmaps. Next, a beta-diversity analysis will be performed comparing the complexity of genera

between subjects. Specifically, three matrices will be created based on weighted and unweighted Bray-Curtis and Unifrac distances that will be used to perform a principal coordinate analysis to highlight the presence of subject clusters based on the complexity of their microbiota.

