The “Linear discriminant analysis effect size” (LEFSE) method will be used to identify taxa that best discriminate between NAFLD-infected and non-infected patients. The LefSE method is an algorithm-based approach that performs the nonparametric Kruskal-Wallis and Wilcoxon rank-sum test to identify bacterial taxa whose relative abundance is statistically different between groups. Then discriminant analysis is applied considering only those bacterial taxa found to be significantly different between the two groups.

EXPECTED RESULTS

The present study is expected to gain new knowledge on the effect of fructose in relation to the onset of obesity-associated liver disease (NAFLD) and bone metabolism, with the identification of new biological, immunological, and omics markers that can be studied in the future as disease targets in the pediatric population. In addition, due to the scientific and sociological interest, the present study aims at the identification of sociodemographic and cultural determinants related to fructose intake, useful for the creation of preventive campaigns aimed at the promotion of a healthy lifestyle, with a change in eating habits that incentivize a healthy diet and a reduction of obesity status in the population. The results obtained, if statistically significant, will ultimately aim to develop effective preventive communication to promote a healthier lifestyle and diet in the population.

ETHICAL ASPECTS

The study was designed and will be conducted in accordance with international and national ethical standards on biomedical research with human beings, specifically:

- *Ethical principles for medical research involving human subjects* (Declaration of Helsinki -World Medical Association, current version);
- European Union *Standards of Good Clinical Practice* (ICH/GCP);
- *Convention on Human Rights and Biomedicine* (Oviedo Convention of 04/04/1997);
- Italian codes of ethics for health professions and specific current national regulations on clinical trials.

Management of informed consent

An information sheet explaining the type of study, purpose, procedures, sample and data collection, and possible benefits and risks of the research is available. This information will be presented to interested persons, who will have the freedom to give consent or to be able to withdraw it when the study has already begun.

Management of sensitive data

The following European and national regulations are kept in mind:

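### Ultrasound speed of sound is read as bone density and compared by fructose intake without regard to adiposity, sex or age band, so a soft-tissue difference could not be told from a bone difference

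*Combined protocol and SAP*

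**What the plan says.** Under Instrumental assessment, the QUS parameters are given direct bone meanings: "specifically speed of sound (SOS) assessing bone density, broadband ultrasound attenuation (BUA) assessing trabecular structure". The text available for review names no skeletal site, device or soft-tissue correction.

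Under Statistical analysis, the whole bone plan is one sentence. Means with SDs, or medians with quartiles, of the "parameters provided by the QUS overall and separately for high and low fructose consumption (below vs above median consumption) will be calculated". No covariate or test is attached to this split. The only stratification mentioned, by age group and center, depends on how many NAFLD cases are seen and is not tied to the QUS summaries.

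The sample is "100 overweight or obese preschool children and adolescents", in two age bands (3 to 6 and 12 to 16 years). The BMI criteria set lower limits and no upper one. Adiposity is measured in several ways: BMI as an SDS, waist and hip circumference and BIA under Clinic-auxological evaluation, and under Instrumental assessment "US ultrasound of the abdomen to evaluate hepatic steatosis, perivisceral and subcutaneous fat". None of these is linked to the QUS analysis.

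The aim is worded descriptively: "the present study aims to describe the composition of bone metabolism according to the level of fructose consumption". Expected results goes further and anticipates "new knowledge on the effect of fructose in relation to the onset of obesity-associated liver disease (NAFLD) and bone metabolism".

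**The concern.** A QUS signal crosses the soft tissue around the bone as well as the bone, so it is plausible that SOS depends partly on that tissue. If the higher- and lower-intake halves differ in fat, a crude comparison of SOS mixes any bone difference with any soft-tissue difference, and nothing in the written plan would separate them. Labelling SOS as bone density hides the ambiguity.

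What is at stake is interpretation. The background section predicts that fructose harms bone, and Expected results speaks of an effect of fructose on bone metabolism. An SOS difference in the predicted direction could be reported as support for that when it partly reflects body composition, sex mix or age mix. No planned figure is wrong, and the sample size is unaffected.

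**Working it through.** **1. The plan's own figure.** The only design figure is the 2.02 g detectable difference in fructose intake between children with and without NAFLD. SD = √9.53 = 3.087. With 25 versus 75, SE = 3.087 × √(1/25 + 1/75) = 0.713. The normal approximation at two-sided 0.05 and 80% power gives (1.960 + 0.842) × 0.713 = 2.00 g, and the noncentral t gives 2.017 g. The figure reproduces. It does not concern QUS, so the bone comparison has no stated precision.

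**2. Precision of the QUS split.** A median split of 100 gives 50 versus 50. In SD units, SE = √(2/50) = 0.20. The 95% CI half-width is 1.984 × 0.20 = 0.40 SD.

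**3. Size of a fat-related shift.** With no true bone difference, the false SOS difference (in SD) is D × s. D is the difference in mean fat between intake halves, in SDs of fat. s is the change in SOS, in SDs, per SD of fat at equal bone. The documents give neither, nor the sign of s, so both ranges are assumed. The last column is the chance of p < 0.05 if a two-sided t-test were run on 50 versus 50; none is planned for this split.

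| D (assumed) | Size of s (assumed) | Size of false SOS difference | Chance of p < 0.05 |
|---|---|---|---|
| 0 | any | 0 | 5% |
| 0.2 | 0.1 to 0.5 | 0.02 to 0.10 SD | 5% to 8% |
| 0.5 | 0.1 to 0.5 | 0.05 to 0.25 SD | 6% to 24% |
| 0.8 | 0.1 to 0.5 | 0.08 to 0.40 SD | 7% to 51% |

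The range runs from nothing to the full CI half-width in step 2. The documents do not show where this study would fall.

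**4. Age mix in the same comparison.** If adolescents made up 60% of one half and 40% of the other, and the age bands differed by 1 to 2 SD in SOS (all assumed), the induced difference would be (0.60 − 0.40) × 1 to 2 = 0.2 to 0.4 SD. This is why the summary should be shown within age band. Doing so does not remove fat differences inside a band.

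**5. Precision within a band.** With equal bands and a band-specific median (assumed), each comparison is 25 versus 25. The half-width is 2.011 × √(2/25) = 0.57 within-band SD.

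**The case against.** The strongest defence is that the bone aim is descriptive and the mechanism is undocumented. Only summary statistics are planned for the intake split. The documents do not say that fat alters SOS at the site used, that the values are uncorrected, or that higher-intake children in this sample carry more fat. With equal fat in the halves the bias is zero.

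Modest assumptions also give a small bias. Take a heel model with 30 mm bone at 1600 m/s, 15 mm soft tissue at 1540 m/s and fat at 1450 m/s, where apparent SOS is total path divided by total transit time. Take a fructose–fat correlation of 0.1 to 0.3 and a heel-fat SD of 1 to 3 mm. For bivariate normal data the gap between halves is 2 × √(2/π) × correlation × SD, or 0.16 to 1.44 mm. That lowers SOS by 0.5 to 4.4 m/s, which is 0.02 to 0.17 SD for an SOS SD of 25 to 30 m/s. Every input is assumed.

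Most of this stands, and it limits the point to an unresolved ambiguity. It does not remove it, because Expected results frames the bone findings as an effect of fructose and the plan has no step that would show whether the halves are comparable in fat.

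The objection also defeats several stronger readings that a reader might infer:

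- *That recruiting only overweight or obese children creates the bias.* A shift common to all children cancels between halves; only a difference between halves matters.
- *That the artefact is about half an SD.* In the heel model, 5 mm of extra fat lowers SOS by 14 m/s, and 14/30 to 14/25 is 0.47 to 0.56 SD. That is the effect of 5 mm of added fat, and nothing in the documents suggests that the halves' means differ by that much.
- *That a finger site would show a large fat effect.* With 8 mm bone at 2300 m/s and 4 mm soft tissue (assumed), 1 mm of added fat lowers SOS by 53.5 m/s, but 1 mm of lean tissue lowers it by 42.0 m/s. So 42.0/53.5, about 78%, comes from adding any soft tissue.
- *That attenuation and amplitude shift in a known direction.* Nothing in the documents supports one.

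**Conclusion.** The point holds in a limited form. The plan equates SOS with bone density and compares QUS by a crude, age-pooled median split, while adiposity data on the same children go unused. A fat-related SOS difference, if present, could not be distinguished from a bone difference. Its size rests wholly on assumptions about the fat difference and the SOS–fat slope, and runs from nil to about 0.4 SD against a CI half-width of about 0.40 SD.

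The documents do not support saying that higher-intake children will appear to have weaker bone, only that the plan could not tell. Nor would it be sound to attribute a difference to bone whenever it survives adjustment. BIA fat and BMI-SDS are proxies for tissue thickness at the measurement site, and adjustment could remove a real effect acting through fat mass. The NAFLD comparison and the sample size are untouched.

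**What to change.** In the bone sentence of Statistical analysis:

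- Report BMI-SDS and BIA fat by intake half.
- Report each QUS parameter by fructose level within each age band (3 to 6 and 12 to 16 years), unadjusted and adjusted for BIA fat mass or BMI-SDS and for sex. State whether the median is overall or band-specific.
- Label the adjusted result a sensitivity analysis, with the proxy and pathway limits given above, and not as proof of a bone effect.

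In Instrumental assessment, describe SOS as a bone-related ultrasound index instead of bone density, and state the site, device and any soft-tissue correction.

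The cost is some wording and one regression per QUS parameter in each band, on data already planned or routinely recorded. The downsides are wider intervals within bands and, in the adjusted version, the possible loss of an effect acting through fat mass, which is why both versions are shown.

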- Children and adolescents with skeletal fragility due to genetic causes;
- Children and adolescents who chronically use drugs capable of altering lipid metabolism and bone remodeling;
- Children and adolescents placed on a diet-therapeutic regimen with dietary styles other than the Mediterranean or Western diet (e.g., ketogenic diet, FoodMap diet, vegan/vegetarian diet) to avoid bias in the interpretation of the microbial signature (the microbial signature of the Western and Mediterranean diets is known in the literature);
- Failure of parents or adolescent (from age 12 years) to give informed consent;

Surgery

No type of surgery

DURATION OF THE STUDY

12-month recruitment and 12-month observation period for sociological survey.

SCDU di Endocrinologia

AOU Maggiore della Carità, [name]

[contact] (Reparto); [contact]

[contact]

Timing of data collection

At the time of recruitment, patients afferent at the Outpatient Endocrinology Clinic of the AOU Maggiore della Carità in Novara, at the Transition Endocrinology Outpatient Clinic of the Endocrinology SCDU, and at the "B. Trambusti" Pediatric Endocrinology Outpatient Clinic of the Giovanni XXIII Children's Hospital will undergo:

Questionnaires to assess the amount of fructose introduced in the diet:

- Questionnaire to assess adherence to the Mediterranean diet in children/adolescents, KIDMED;
- Questionnaire to assess food frequency in children, IDEFICS;
- 24h recall questionnaire, to collect information regarding meals taken in the previous 24 hours. The amount of macronutrients will be obtained through dedicated software "Dietosystem Professional Food Therapy Software" from DSMedica. The questionnaire is added with specific questions and figures to identify the portions of foods and put them in relation to the amount of fructose intake;
- Calculation of the Dietary Inflammatory Index (DII) using a list of foods. This parameter makes it possible to define the extent to which a dietary pattern is able to promote the synthesis of pro-inflammatory molecules (17,18);
- Sociological questionnaire prepared ad hoc by Unit 3 to assess diet and fructose intake in relation to family socioeconomic status.

Anamnestic evaluation

- The patient's mother will be asked about the gestational age, mode of delivery and anthropometric data of the child at birth.
- Detection of current drug therapy (if any).

Instrumental assessment

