Biochemical parameters according to clinical practice will be analyzed at the laboratories of Maggiore della Carità Hospital in Novara and at the laboratories of Giovanni XXIII Children's Hospital in Bari by estimation with Siemens Advia 2400 Healthcare Diagnostics, Siemens ADVIA chemistry XPT and in accordance with the respective protocols of reagent use.

Metaproteomic and metabolomics analysis will be conducted on stool, plasma and urine samples stored during the study for omics signature designation. Metaproteomic analysis with UPHLC-MS/MS mass spectrophotometer will be performed on stool samples to identify the presence of microorganisms in the gastrointestinal tract to be then correlated with the diet followed and clinical parameters of the patients. Peptides identified by the analysis will be entered into the UniProtKB, KEGG database and used for phylogenetic analysis.

Metabolomic analysis will be carried out on all three types of samples; metabolomics conducted on fecal samples will allow assessment of the functional activity of microorganisms, characterizing the intermediate phenotype that mediates host-microbiome interactions. Using one-dimensional gas chromatograph coupled with mass spectrometer (GC-MS-SPME), the metabolic profile and changes in metabolite levels in association with fructose intake will be identified. The identification of the main SCFAs will be carried out with the same instrument and then confirmed by injecting the appropriately treated samples into the instrument, comparing the retention time and the corresponding spectra obtained from GC-MS analysis. This method allows a metabolomic signature to be defined in relation to fructose consumption.

SAMPLE SIZE AND STATISTICAL METHODS

The study plans to enroll 100 children afferent to the centers previously listed. Given a first-type error of 0.05, a power of 80%, a variance of equal fructose consumption in the groups of children with and without NAFLD of 9.53 (pooled variance obtained from data reported in the article by Nier et al. (20), a ratio of 1:3 between children with and without NAFLD (expected prevalence in overweight and obese children ~24% (21)), the sample size will allow to highlight as statistically significant a minimal difference in the averages of fructose consumption between healthy and diseased children of 2.02 grams.

Statistical analysis

Evaluation of the relationship between fructose and NAFLD

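### Fructose is compared between children with and without NAFLD in unadjusted grams, and no planned analysis tests whether it differs at equal total energy intake

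*Combined protocol and SAP*

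**What the plan says.** Under Sample size and statistical methods, the combined protocol and SAP enrols 100 children, with one child with NAFLD to every three without. It assumes "a variance of equal fructose consumption in the groups of children with and without NAFLD of 9.53" and concludes that the sample can detect "a minimal difference in the averages of fructose consumption between healthy and diseased children of 2.02 grams". The target is thus in absolute grams.

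Under Statistical analysis (evaluation of the relationship between fructose and NAFLD), "the t-test or the Mann-Whitney test will be used to test the difference in fructose consumption between children with NAFLD and those without the disease". The same tests are applied to the remaining numerical variables. Stratification by age group and by centre will be considered, depending on how many NAFLD cases are seen. No regression is planned for this question. The protocol nowhere mentions total energy, fructose per unit of energy or scaling of intake to body size.

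Under Timing of data collection, a 24-hour recall is taken: "The amount of macronutrients will be obtained through dedicated software". Extra questions and pictures on portions link foods to fructose. Total energy is not named as an output.

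The Aims section sets out to study the impact of fructose on liver complications. Expected results speaks of an effect of fructose and foresees preventive messages if results are significant.

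**The concern.** Grams of a nutrient tend to rise with the total amount eaten. Suppose children with NAFLD eat more of everything, with the same diet composition. Their mean fructose intake in grams is then higher, although fructose has no special place in their diet. An unadjusted comparison in grams gives the same answer in that case as when their diet really is richer in fructose.

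The two explanations lead to different messages: one about fructose, the other about overall intake. Because the protocol intends to draw on the result for prevention, a significant gram difference could be read as specific to fructose when the analysis has not tested that.

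**Working it through.** **Inputs from the protocol.** N = 100 in a 1:3 ratio, so 25 with and 75 without NAFLD; variance 9.53, so SD = √9.53 = 3.087 g; alpha 0.05; power 80%. Sidedness is not stated, but two-sided reproduces the plan's figure.

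**Step 1: reproduce 2.02 g.** Standard error of the difference = 3.087 × √(1/25 + 1/75) = 0.713 g. The normal approximation gives 0.713 × (1.960 + 0.842) = 1.997 g. The noncentral t with 98 degrees of freedom gives 2.017 g, which rounds to 2.02. The sample-size arithmetic is correct on its own inputs. An observed difference of 1.984 × 0.713 = 1.41 g is already significant.

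**Step 2: what general excess of food equals 2.02 g?** If children with NAFLD eat a fraction x more of everything at the same composition, the expected fructose difference is x × M, where M is mean fructose intake in the group without NAFLD. The excess that gives the target is x = 2.02 / M. The documents give no M, so every value below is an assumption.

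| Assumed M | 2.02 / M | Implied coefficient of variation, 3.087 / M |
|---|---|---|
| 10 g | 20.2% | 31% |
| 20 g | 10.1% | 15% |
| 30 g | 6.7% | 10% |
| 40 g | 5.0% | 8% |
| 60 g | 3.4% | 5% |

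**Step 3: chance that a general excess alone is significant, with the plan's SD.** Two-sided t-test, 25 against 75, SD 3.087 g, true difference x × M:

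| Assumed M | 5% more food | 10% more food |
|---|---|---|
| 10 g | 0.5 g: 11% | 1.0 g: 28% |
| 20 g | 1.0 g: 28% | 2.0 g: 79% |
| 30 g | 1.5 g: 55% | 3.0 g: 99% |
| 40 g | 2.0 g: 79% | 4.0 g: over 99% |

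**Step 4: let the SD vary as well.** The last column of the first table shows that a mean of 20 to 40 g with an SD of 3.09 g implies a coefficient of variation of only 15% to 8%. That is narrow for intake pooled over ages 3 to 6 and 12 to 16. If the SD is instead set as a fraction of the mean (CV), the standardised difference is x / CV and M drops out:

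| Assumed CV | 5% more food | 10% more food | 20% more food |
|---|---|---|---|
| 20% | 19% | 57% | 99% |
| 30% | 11% | 30% | 82% |
| 50% | 7% | 14% | 40% |

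**Step 5: do other planned analyses separate the two explanations?**
- Stratification by age group and centre is conditional on the number of NAFLD cases. If done, it removes differences in intake due to age or centre, but not those within a stratum.
- The group tests of other numerical variables could show that children with NAFLD eat more or are heavier. They are separate and unadjusted, so they do not estimate the fructose difference at a given energy intake.

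**The case against.** The strongest reply is that grams are a defensible exposure. The Study design section asks about the relationship between fructose consumption and NAFLD, and the mechanism in the introduction concerns the fructose load on the liver. On that reading the absolute amount is the right quantity. This stands: the gram comparison is not an error and should remain. It does not cover the further step, in Expected results, to an effect of fructose as such.

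Second, the plan is not silent on the rival explanation, because dietary and anthropometric variables are also compared between groups. This stands in part. A reader might infer that the plan yields no information at all on overall intake; that is too strong. It lacks an analysis of fructose at equal energy.

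Third, a reader might infer that children with NAFLD who eat only 5 to 10% more would probably produce the whole target difference. The documents do not support that. It needs a mean of about 20 to 40 g, which they do not give, together with the plan's small SD, and the probabilities fall sharply if the spread is wider. Nor do the documents show that children with NAFLD in this overweight or obese sample eat more than the others.

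Finally, energy is not named as a recall output, and the protocol does not say that the gram figure comes from the recall alone. Energy can be derived from macronutrients, but the source of the fructose figure should be stated.

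**Conclusion.** The point holds as a gap in the analysis. Fructose is sized and tested in unadjusted grams, and nothing planned tests it at equal total energy, so a positive result could not be attributed to fructose as distinct from overall food intake.

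The size is uncertain. The general excess equivalent to 2.02 g runs from about 20% to 3.4% over assumed means of 10 to 60 g. The chance that a 10% excess alone is significant is 28%, 79% or 99% at means of 10, 20 or 30 g with the plan's SD, and about 30% or 14% with an assumed coefficient of variation of 30% or 50%. These figures assume identical diet composition in the two groups, a 25 to 75 split and a two-sided t-test.

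The sample-size calculation is not faulted here. The narrow implied spread might suggest that the variance is wrong, but it follows from assumed means and proves nothing about the source figure. The change is advisable and cheap; the study is not invalid without it.

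**What to change.** In the statistical analysis section, keep the gram comparison as the analysis that sizes the study. Beside it, prespecify one energy-adjusted analysis from the same 24-hour recall: preferably a linear regression of fructose on NAFLD status with total energy and age group as covariates, reporting the adjusted difference and its 95% confidence interval. State that fructose grams for this analysis come from the recall and that total energy is derived from its macronutrients.

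Fructose per 1000 kcal may be added as a sensitivity analysis. It is not equivalent to the regression, because a ratio assumes that fructose is proportional to energy and a covariate does not. Word any conclusion about fructose specifically, as distinct from overall intake, in light of the adjusted estimate and its interval, without making a second significant test a condition.

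The cost is a short addition to the text and one extra analysis of data already collected. The 2.02 g detectable difference does not apply to it. Its power cannot be computed here, because the documents give no mean or SD of energy intake and no correlation between fructose and energy. The adjusted estimate may also be less favourable than the difference in grams.
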